6.2.2 In-hospital Clinical Safety and Efficacy

The following end-points will be measured through hospital discharge:

- In-hospital Major Adverse Cardiac Events (MACE), a composite of:
 - All death (cardiac and non-cardiac)
 - Myocardial infarction (MI)
 - Target Lesion Revascularization (TLR), clinically indicated
- Individual components of the MACE composite end-point
- In-hospital Target Lesion Failure (TLF) a composite of:
 - Cardiac death
 - Target vessel MI
 - TLR, clinically indicated
- In-hospital stent thrombosis (ST) within the target vessel
- Clinically significant arrhythmias (requiring intervention)

Both MI and ST are to be determined by the Academic Research Consortium (ARC) classification criteria.⁸ MI to be classified into various types and include the 99th percentile upper reference limit (URL) decision limits for biomarkers employed.⁹

Myocardial Infarction will be defined as:

- Q-Wave MI: Development of new (i.e., not present on the subject's ECG before allocation) pathological Q-waves in 2 or more leads lasting 0.04 seconds with post-procedure CK-MB levels elevated above normal.
- Non-Q-Wave MI: Elevation of post-procedure CK-MB levels to >3.0 times ULN without new Q-waves.

For subjects undergoing bypass surgery, a peri-operative MI will be defined as follows:

- a) Total CK-MB $>5\times$ ULN.
or
- b) Presence of new pathologic Q-waves as defined above.

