### 7.2 Summary of Study Data

The baseline demographic and lesion characteristics and angiographic and clinical outcomes will be evaluated by descriptive statistics. These calculations will be performed under the assumption that the data are in a normal distribution. All continuous variables will be summarised using the following descriptive statistics: n (non-missing sample size), mean and standard deviation. The frequency and percentages (based on the non-missing sample size) of observed levels will be reported for all categorical measures. Deaths, Serious Adverse Events and other Significant Adverse Events will be reported as number and percentage. All analyses will be performed using SAS version 9.4 (NC, USA).

---

Lesion related outcomes were assessed using core lab data. Where core lab was not analyzable, site reported data were used. No outcomes were imputed.

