Hypertension (requiring treatment)	
No	
Yes	
Peripheral arterial disease (arms, legs, renal, mesenteric, aneurysm)	
No	
Yes	
Previous history of stroke more than 6 months prior	

	Overall population N = patients
No	
Yes	
Prior myocardial infarction	
No	
Yes	
Previous PCI	
No	
Yes	
Previous CABG	
No	
Yes	
Left ventricular ejection fraction	
30-40%	
>40%	
Unknown	
Angina status	
Asymptomatic	
NSTEMI	
Stable angina	
Unstable angina	
CCS Class	
0	
I	
II	
III	
IV	
Heart failure NYHA class III or IV	
No	
Yes	
Extent of coronary artery disease (number of vessels with CAD >= 50%)	
1	
2	
3	
BASELINE MEDICATIONS	
ACE inhibitors or ARB	
No	
Yes	
Beta-blockers	
No	
Yes	
Calcium channel blockers	

	Overall population N = patients
No	
Yes	
Long-acting nitrate	
No	
Yes	
Ranexa	
No	
Yes	
Oral Anticoagulation	
No	
Yes	
Statins	
No	
Yes	
Proton pump inhibitor	
No	
Yes	
Aspirin	
No	
Yes	
P2Y12 Inhibitor	
Clopidogrel	
None	
Prasugrel	
Ticagrelor	
BASELINE LABS	
Creatinine	
N, N Missing	
Mean ± Std	
Min , Max	
Median (IQR)	
Hemoglobin	
N, N Missing	
Mean ± Std	
Min , Max	
Median (IQR)	
White cell count (10  /L)	
N, N Missing	
Mean ± Std	
Min , Max	
Median (IQR)	

	Overall population N = patients
Platelets	
N, N Missing	
Mean ± Std	
Min , Max	
Median (IQR)	
Troponin	
N, N Missing	
Mean ± Std	
Min , Max	
Median (IQR)	
CKMB	
N, N Missing	
Mean ± Std	
Min , Max	
Median (IQR)	
BASELINE ECG	
12-lead electrocardiogram performed	
No	
Yes	
Rhythm	
AF/flutter	
Other	
Sinus Rhythm	
Q wave	
No	
Yes -Existing	
ST-segment depression or elevation	
No	
Yes - Existing	
Yes - New	

Table 4: Discharge patient data

	Overall population N = patients
DISCHARGE	
Did any complications occur before discharge	
No	
Did the patient complete all study related activities at the time of discharge?	
No	
Yes	
Was there a protocol deviation?	
No	
Yes	
DISCHARGE CARDIAC ENZYMES	
Troponin	
N, N Missing	
Mean $\pm$ Std	
Min , Max	
Median (IQR)	
CKMB (Immediately after procedure)	
N, N Missing	
Mean $\pm$ Std	
Min , Max	
Median (IQR)	
CKMB (6-12h after PCI)	
N, N Missing	
Mean $\pm$ Std	
Min , Max	
Median (IQR)	
CKMB (18-24h after PCI or prior to discharge)	
N, N Missing	
Mean $\pm$ Std	
Min , Max	
Median (IQR)	
POST PCI LABS	
Lowest Hemoglobin value	
N, N Missing	
Mean $\pm$ Std	
Min , Max	
Median (IQR)	
Highest Creatinine value	
N, N Missing	
Mean $\pm$ Std	

	Overall population N = patients
Min , Max	
Median (IQR)	

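### CK-MB is tabulated without ULN scaling or a per-patient peak, so the SAP's enzyme rows cannot be read against the protocol's ULN-based MI limits

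*SAP*

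**What the plan says.** **Tables.** SAP Table 3 has one baseline row each for troponin and CK-MB. Table 4 has one troponin row with no time point and three CK-MB rows: immediately after the procedure, "CKMB (6-12h after PCI") and "CKMB (18-24h after PCI or prior to discharge"). Each row takes N, N missing, mean and SD, minimum and maximum, and median (IQR), for the overall population. None shows a unit, a ULN, a multiple of ULN, a count above a limit, or the highest of the three draws.

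**Summary rule.** SAP 7.2 states: "All continuous variables will be summarised using the following descriptive statistics: n (non-missing sample size), mean and standard deviation". It adds: "These calculations will be performed under the assumption that the data are in a normal distribution". It contains no rule for putting laboratory values on a common scale.

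**MI definition.** Protocol 6.2.2 uses CK-MB only relative to the laboratory's limit:
- Q-wave MI needs new Q-waves with "post-procedure CK-MB levels elevated above normal".
- Non-Q-wave MI is "Elevation of post-procedure CK-MB levels to >3.0 times ULN without new Q-waves".
- A separate rule, introduced by "For subjects undergoing bypass surgery, a peri-operative MI will be defined as follows", uses 5 times ULN or new Q-waves.

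The same section also calls for "99th percentile upper reference limit (URL) decision limits for biomarkers employed".

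**Laboratories.** Up to five US sites enrol 60 subjects. Protocol 6.3 names a core laboratory for angiography. No central biochemistry laboratory or common assay is named.

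**The concern.** Three scheduled post-procedure draws per patient are the plan's quantitative record of myocardial injury, and acute safety is a stated aim of the study. The protocol reads those draws on one scale (multiples of ULN) and the SAP tabulates them on another.

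Two things follow. First, whatever assays are used, a reader of Table 4 cannot tell how the values stand against 1x or 3x ULN, or how many patients crossed either line at any draw. Rises between 1x and 3x ULN without new Q-waves do not meet the protocol's CK-MB criteria for MI outside bypass surgery, so the enzyme rows are the natural place for them to appear. Second, if sites use assays with different limits, a pooled mean, SD, median or maximum depends partly on which hospital contributed the patient.

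**Working it through.** The documents give no ULN, unit, expected CK-MB value or MI rate, so there is no planned figure to reproduce. Every ULN and distribution below is an assumption, shown over a range.

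**1. The three time-point rows do not yield the peak.** Suppose three patients each exceed 3x ULN once, at different draws. Alternatively, suppose one patient exceeds it at all three draws and the other two never do. With the same set of values at each draw, every row of Table 4 is identical in the two cases. Yet three patients have crossed the limit in one case and one in the other. This holds even with a single assay.

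**2. A raw value has no fixed meaning without its ULN.** Multiple = raw / ULN. For a raw CK-MB of 15:

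| Assumed ULN | Multiple of ULN | Raw value at 3x ULN |
|---|---|---|
| 4 | 3.75 | 12 |
| 5 | 3.0 | 15 |
| 6 | 2.5 | 18 |
| 8 | 1.88 | 24 |
| 25 | 0.6 | 75 |

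**3. Effect on the pooled mean if ULNs differ.** Assume CK-MB/ULN is log-normal with median 0.6 and log-SD 0.7 at every site, so injury is the same everywhere. The mean multiple is 0.6 × exp(0.7²/2) = 0.77. Pooled raw mean = 0.77 × average ULN. Move the share of patients on the higher-ULN assay from 20% to 80%:

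| Assumed ULNs | Average ULN | Raw mean | Change |
|---|---|---|---|
| one common value | unchanged | unchanged | 0% |
| 4 and 6 | 4.4 to 5.6 | 3.4 to 4.3 | 27% |
| 4 and 8 | 4.8 to 7.2 | 3.7 to 5.5 | 50% |
| 5 and 25 | 9 to 21 | 6.9 to 16.1 | 133% |

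The mean multiple of ULN stays at 0.77 throughout.

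**4. Effect on ranking.** This was simulated for 5 sites of 12 patients, with a common log-normal CK-MB/ULN (median 0.7, log-SD 0.8) and 4,000 repeats. The table covers runs with at least one patient above 3x ULN. It gives the proportion in which some patient below the limit had a higher raw value than one above it:

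| Assumed site ULNs | Proportion of runs |
|---|---|
| 5 at all sites | 0% |
| 4 to 6 | 20% |
| 4 to 8 | 42% |
| 5 at three sites, 25 at two | 81% |

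On the ULN scale the summary barely moves: mean about 0.96 and about 2 of 60 patients above 3x in every scenario.

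**5. How many patients the missing counts might describe.** Expected number above c × ULN = 60 × [1 − Φ(ln(c/median)/log-SD)].
- Median 0.6, log-SD 0.7: above 1x, 60 × 0.233 = 14.0; above 3x, 60 × 0.0107 = 0.6; between them, 13.3.
- Median 0.7, log-SD 0.8: above 1x, 60 × 0.328 = 19.7; above 3x, 60 × 0.0344 = 2.1; between them, 17.6.

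Under these assumptions about 13 to 18 of 60 patients would have a value between 1x and 3x ULN, against roughly 1 to 2 above 3x. The first group has no count anywhere in the tables.

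**The case against.** **No endpoint rests on these rows.** This is the strongest objection, and it stands. Protocol 6.4 has an independent committee adjudicate the clinical endpoints under the protocol's definitions. Table 9 reports MACE, MI and TLF in their own right. The primary endpoint contains no biomarker, and the study tests no hypothesis. A reader might infer that MI or MACE is miscounted because CK-MB is pooled raw. The documents do not support that: the ULN rule applies to each patient's value, not to the pooled summary.

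**Different assays are not documented.** This also stands. A reader might infer that Tables 3 and 4 do mix assays and so cannot show injury at all. Several sites and no named central biochemistry laboratory make mixing possible, but the documents do not say that it occurs. The wording about biomarkers employed concerns how MI is classified, not differences between hospitals. With one ULN the pooling effect is nil, and the 5-versus-25 case is an assumed extreme.

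**Missing units are not specific to cardiac markers.** Correct. Creatinine, hemoglobin and platelets also lack units in Table 3, so the missing unit is weak evidence. The missing ULN scale and peak carry the point.

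**Troponin is a side issue.** Largely correct. The protocol gives no troponin multiple, uses troponin before the procedure only as an eligibility fallback, and schedules no post-procedure troponin draw. Rescaling would not supply the time point that the Table 4 row lacks.

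**Some of the information is already shown.** Partly. Median (IQR) is in the mock tables, which limits the harm from SAP 7.2's normality assumption. If there were one assay and its ULN were printed, the maximum would show whether anyone crossed 3x. It would still not show how many patients did, or how many lay between 1x and 3x.

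**Conclusion.** The point holds as a weakness in the descriptive safety tables. CK-MB is tabulated on a scale the protocol does not use, and the per-patient peak is absent. As laid out, the rows cannot be set against the 3x ULN limit or show how many patients had sub-threshold rises. That part needs no assumption about assays.

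The further effect, that pooled values partly reflect the laboratory, is conditional on ULNs differing between sites. Its size runs from nil with one ULN, through 27% on the mean for assumed ULNs of 4 and 6, to 133% for 5 and 25. These figures also assume the same log-normal distribution of CK-MB/ULN at every site.

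The adjudicated MI, MACE and TLF results and the primary endpoint are unaffected. For troponin the case is weaker, and is mainly one of labelling. The change is worth making because it is a better summary at little cost, not because a conclusion of the study is at risk.

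**What to change.** In SAP 7.2 and Tables 3 and 4:
- Report CK-MB as a multiple of the performing laboratory's ULN, with median (IQR) as the main summary.
- Add each patient's peak post-procedure CK-MB/ULN, with n (%) above 1x and above 3x ULN. A count above 5x is optional, since the protocol uses that limit only for bypass surgery. The >3x count will overlap with non-Q-wave MI in Table 9 and serves as a check on it.
- Where troponin is available, report it as a multiple of the assay's 99th percentile URL, and label the Table 4 row as unscheduled.
- State how many patients contribute to the baseline CK-MB row. Protocol 5.3.2 requires CK-MB before the procedure only if total CK is abnormal, so that row may describe a selected subset.

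Cost: SAP wording, a few derived variables, and a record of each site's assay limit. The MI definition already needs the CK-MB ULN. No additional blood draws or patient visits are involved.
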